### **3.2.3.4 Confirmed/Suspected COVID-19 infections**

Confirmed/Suspected Covid-19 infection is defined as an AE occurring during the pandemic timeframe (after 11th of March 2020) with preferred term within the AE search criteria

developed by the latest MedDRA maintenance and support service organization (MSSO) guidance.

### 3.2.4 Electrocardiograms

These measurements are recorded as detailed in the study schedule (See [Appendix A](#)). If vital signs, ECG and blood draws for laboratory tests are scheduled at a visit, they will always be performed in the order: ECG, vital signs and then blood draws.

At Screening, and as clinically indicated throughout the study, ECGs should be obtained after the patient has been in a supine position for 5 minutes and recorded while the patient remains in that position. From these resting 12-lead ECGs values of the QT and RR intervals and the QT interval corrected for heart rate using Fridericia's correction (QTcF) is derived using the following formula:

- $QTcF = QT/RR^{(1/3)}$  where RR is in seconds

In case of clinically significant ECG abnormalities, 2 additional 12-lead ECGs will be performed. All three ECGs should include a value of QTcF over a brief period (eg, 30 minutes). A QTcF value >470 msec will confirm the ECG abnormality finding.

The value of QTcF will be re-derived from the values of RR and QT during the creation of the reporting database.

### 3.2.5 Vital Signs

Vital signs measurements will be collected at the start of each treatment cycle as detailed in the schedule of assessment ([Appendix A](#)).

Measurements will include SBP (mmHg), DBP (mmHg), pulse rate (breaths/min), weight (kg), body temperature (degrees Celsius), and respiratory rate (breaths/min).

### 3.2.6 Laboratory Data

Laboratory data (clinical chemistry, haematology and urinalysis) will be collected at the start of each treatment cycle as detailed in the schedule of assessment ([Appendix A](#)). Coagulation will be reported as clinically indicated. Laboratory data will be from local laboratories and will be converted to AZ preferred units, and AZ durvalumab project reference ranges will be used for the primary interpretation of laboratory data.

Corrected calcium product will be derived during creation of the reporting database using the following formula:

$$\text{Corrected calcium (mmol/L)} = \text{Total calcium (mmol/L)} + ([40 - \text{Albumin (g/L)}] \times 0.02)$$

### 3.2.7 Physical Examination

A physical examination will be performed at Screening and during the study. Findings in this

data will be reported as medical history at Screening. Any new or aggravated clinically relevant abnormal medical finding at a physical examination as compared with the baseline assessment will be reported as an AE unless unequivocally related to the disease under study.

### 3.2.8 Exposure to Durvalumab

The total (or intended) exposure (weeks) of durvalumab is defined as:

- Total treatment duration (weeks) = Total treatment duration (days) / 7

where:

Total treatment duration (days) = [earliest of (last dose date where dose > 0mg + 27 days, death date, cut-off date [DCO]) - first dose date] + 1

The actual exposure (weeks) of durvalumab is defined as:

- Actual treatment duration (weeks) = [total treatment duration (days) – total duration of dose delays (days)] / 7.

Dose reductions are not permitted per the CSP for durvalumab and the actual exposure calculation makes no adjustment for any dose reductions that may have occurred.

As patients are scheduled to receive 1500 mg via IV infusion every 4 weeks (28 days), the duration of dose delays is the sum of all individual dose delays as follows:

- Total duration of dose delays (days) = sum of MAX[0, (date of dose [x+1] – date of dose [x] - 28 days)].

If no delays were encountered, the total duration of dose delays would sum up to 0.

Relative dose intensity (RDI) is the percentage of the actual dose intensity delivered relative to the intended dose intensity through to treatment discontinuation.

RDI is defined as follows:

RDI = 100% \* d/D, where d and D are, respectively, the actual and intended cumulative doses delivered up to the date of durvalumab discontinuation or progressive disease or the data cut-off date, whichever occurs earlier. D is the total dose that would be delivered if there were no modification to dose or schedule.

Percentage intended dose (PID) is the percentage of the actual dose delivered relative to the intended dose through to disease progression.

PID = 100% \* d1/D1, where d1 is the actual cumulative dose delivered up to the earlier of progression (or a censoring event) or the data cut-off date and D1 is the intended cumulative dose up to the earlier of progression (or a censoring event) or the data cut-off date. D1 is the total dose that would be delivered, if there were no modifications to dose or schedule.

When deriving actual dose administered the volume before and after infusion will also be considered.

To illustrate the calculation of RDI, [Table 5](#) shows an example of durvalumab dosing for 4 patients.

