1.2 Schedule of assessments

The procedures for the screening and treatment periods in this study are presented in [Table 1](#), and the procedures for the follow-up period are presented in [Table 2](#) (Schedule of assessments [SoA]).

Whenever vital sign assessments and blood draws are scheduled for the same nominal time, the assessments should occur in the following order: vital signs and then blood draws. Whenever electrocardiograms (ECGs), vital signs assessments, and blood draws are scheduled for the same nominal time, the assessments should occur in the following order: ECG, vital sign assessments, and then blood draws.

Patients may delay dosing due to immune-mediated adverse events (imAEs) or non-imAEs or for reasons other than TRAE.

- In case of imAEs or non-imAEs, dosing may be delayed per the Dosing Modification and Toxicity Management Guidelines (Section [8.4.5](#)).
- If dosing must be delayed for reasons other than TRAEs, dosing will resume as soon as feasible.

One cycle of treatment with the IP is equal to 28 calendar days.

Dosing intervals of subsequent cycles may be shortened as clinically feasible in order to gradually align treatment cycles with the schedule of tumour efficacy (RECIST) and PRO assessments. Subsequent time between 2 consecutive doses cannot be less than 22 days, based on the half-life of durvalumab (MEDI4736) (see current Investigator Brochure [IB]).

If imaging procedures were performed for alternate reasons prior to signing consent, these can be used for screening purposes with consent of the patient. However, all screening imaging results must have been obtained within 28 days of first IP dose administration.

PROs and tumour efficacy (RECIST) assessment dates are not affected by dose delays and remain as originally scheduled, as they are based on the date of first IP administration (not the date of therapy).

All other scheduled assessments must be performed relative to the start of the dosing cycle such that all laboratory procedures, etc, required for dosing should be performed within 3 calendar days prior to dosing.

| | Screening | C1 ^a | C2 ^a | C3 ^a | C4 ^a | C5 to PD (max. 24 months) ^{a,b} | | For details see Section | |
|------------------------------------|-----------|-----------------|--|-----------------|-----------------|--|-------------|-------------------------|-----|
| Week | -4 to -1 | 1 | q4w ±3 days unless dosing needs to be held for toxicity reasons | | | | Final visit | | |

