| Day | -28 to -1 | 1 | q28d ±3 days unless dosing needs to be held for toxicity reasons | | | | | | |
| Pregnancy test ^l | X | X | X | X | X | X | X | 8.2.1 | |
| Monitoring | | | | | | | | | |
| CCI | X | X | X | X | X | X | X | 8.2.6 | |
| AE/SAE assessment ^m | ←-----→ | | | | | | | | 8.3 |
| Drug accountability | | X | All visits | | | | | | 6.3 |
| IP administration | | | | | | | | | |
| Durvalumab (MEDI4736) ⁿ | | X | X | X | X | X | X | 6.1 | |
| QoL assessments | | | | | | | | | |
| CCI | X | X | X | X | X | X | X | 8.1.2.1, 8.1.2.2 | |
| CCI | X | X | X | X | X | X | X | 8.1.2.3 | |
| Biomarker assessments | | | | | | | | | |
| CCI | X | | | | | | | 8.8.1.1 | |
| CCI | X | | | | | | | 8.8.1.1 | |
| CCI | X | X | X | X | | | | 8.8.1.2 | |
| CCI | | X | | | | | | 8.7.1 | |

| | Screening | C1 ^a | C2 ^a | C3 ^a | C4 ^a | C5 to PD (max. 24 months) ^{a,b} | | |
|--|-----------|--|--|-----------------|-----------------|--|-------------|-------------------------|
| Week | -4 to -1 | 1 | q4w ±3 days unless dosing needs to be held for toxicity reasons | | | | Final visit | For details see Section |
| Day | -28 to -1 | 1 | q28d ±3 days unless dosing needs to be held for toxicity reasons | | | | | |
| Efficacy evaluations | | | | | | | | |
| Tumour evaluation as per local institutional standard care (CT or MRI) (RECIST 1.1) ^{b,s} | X | The allowed window for the tumour assessment is ±7 days. On-study tumour assessments begin 8 weeks ±1 week after IP treatment initiation and continue q8w ±1 week through 52 weeks (relative to the date of IP treatment initiation) and q12w ±1 week thereafter (relative to the date of IP treatment initiation) until disease progression, plus an additional follow-up scan is performed if clinically feasible. The on-study imaging schedule of 8 weeks ±1 week through 52 weeks and then q12w ±1 week thereafter MUST be followed regardless of any delays in dosing. Additional scans can be completed per standard practice post disease progression. | | | | | 8.1 | |

^a These cycles refer to the 28-day cycles of administration of durvalumab (MEDI4736).

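### The SAP's dose-delay formula ignores the ±3-day dosing window, so a patient with no late dose can accrue delay and lose actual exposure

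*SAP*

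**What the plan says.** SAP 3.2.8 (Exposure to Durvalumab) defines the total duration of dose delays as "sum of MAX[0, (date of dose [x+1] – date of dose [x] - 28 days", evaluated for each pair of consecutive doses, and then states: "If no delays were encountered, the total duration of dose delays would sum up to 0". Delay feeds directly into exposure: "Actual treatment duration (weeks) = [total treatment duration (days) – total duration of dose delays (days)] / 7". The duration it is taken from is "Total treatment duration (days) = [earliest of (last dose date where dose > 0mg + 27 days, death date, cut-off date [DCO]) - first dose date] + 1". SAP 1.2.1 (Study Treatment) says that delays count as non-exposure time.

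Protocol 1.2 (Schedule of assessments, Table 1) sets the dosing schedule as "q28d ±3 days unless dosing needs to be held for toxicity reasons". The same section adds: "Dosing intervals of subsequent cycles may be shortened as clinically feasible in order to gradually align treatment cycles", subject to a floor: "Subsequent time between 2 consecutive doses cannot be less than 22 days". It does not say whether the ±3 days run from the first dose or from the previous one.

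Actual exposure is a listed summary in SAP 4.5.5 (Exposure). Summed over patients, it is the denominator of the AE rate per 100 patient-years in SAP 4.5.1 (Adverse Events).

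**The concern.** The schedule treats a few days' scatter as ordinary and a hold for toxicity as something different. The delay formula does not make that distinction. A dose given early, which the protocol allows, makes the next interval long even when the next dose falls exactly on its scheduled day, and the extra days are booked as delay. Early days earn no credit, so scatter accumulates in one direction.

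At stake are the reported actual exposure and the AE rate per 100 patient-years, which rises as its denominator falls. A patient for whom the investigator recorded no delay can still lose exposure to a computed one.

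**Working it through.** **Inputs from the documents.** Delay, actual exposure and total duration as defined in SAP 3.2.8; a window of 28 ± 3 days and a minimum interval of 22 days (Protocol 1.2); up to 26 doses, hence 25 intervals (Protocol 6.1.2). The distribution of dose dates within the window is not given and is assumed below.

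**The SAP's own statement.** For 26 doses exactly 28 days apart, every term is MAX(0, 28 − 28) = 0 and the total is 0. The statement holds in that case.

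**A patient with no late dose.** Scheduled days are 1, 29 and 57; doses are given on Days 1, 26 and 57, so the second is 3 days early and the third on its day.
- Intervals: 25 and 31 days. Delay = 0 + 3 = 3 days.
- Total duration = (57 + 27 − 1) + 1 = 84 days = 3 × 28.
- Actual exposure = 84 − 3 = 81 days.

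**Direction.** When the end date is the last dose + 27 days, total duration = 28 × doses + (days late − days early), summed over intervals. Subtracting the days late leaves actual exposure = 28 × doses − days early. Scatter can lower this but never raise it. In the example, 84 − 3 = 81.

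**Average size, base case (assumption).** The first dose is on Day 1; each later dose is independently uniform on −3 to +3 days around a fixed 28-day grid.
- Expected delay per interval between two scattered doses: 56/49 = 1.143 days. First interval: 6/7 = 0.857 days.
- 7 doses: 0.857 + 5 × 1.143 = 6.6 days.
- 13 doses: 0.857 + 11 × 1.143 = 13.4 days.
- 26 doses: 0.857 + 24 × 1.143 = 28.3 days; 95% of simulated patients lie between 20 and 38.
- Share of exposure at 26 doses: 28.3/728 = 3.9%. Rate inflation: 728.0/699.7 − 1 = 4.0%.

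**Other assumptions, 26 doses, mean delay.**

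| Scatter | Days |
|---|---|
| Triangular over ±3, fixed grid | 22.0 |
| Uniform ±3 counted from the previous dose | 21.4 |
| Always 0 to 3 days late, fixed grid | 16.5 |
| 72% of doses exactly on the day, fixed grid | 9.7 |

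Two further cases fall outside this band. Mostly on-the-day dosing counted from the previous dose gives 5.5 days. Dosing always 0 to 3 days late after the previous dose gives 37.5, but there the course itself slips by 37.5 days on average, so that figure is real lateness.

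**Possible range for a 26-dose patient within the window.** Minimum 0, if no interval exceeds 28 days. Maximum on a fixed grid, alternating +3 and −3: one step of 3 and twelve of 6 = 3 + 72 = 75 days. The intervening short intervals are 22 days, which the protocol permits.

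**The case against.** The strongest reply is that this is a convention and not an error. The SAP anchors delay to a 28-day schedule, and the zero-delay sentence is true if no delay means that no interval exceeds 28 days. Actual exposure then equals the number of days lying within 28 days of a dose, which is coherent, and no document states a true value that it misses. This stands in part: the arithmetic is consistent with the formula. However, the SAP calls the quantity dose delay, and SAP 1.2.1 describes delay as something caused by a TRAE or another reason. Days 1, 26 and 57 contain no such event.

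Three stronger readings are tempting, and the documents do not support them.
- A reader might infer that every patient kept within the window loses about four weeks. That figure is a mean that needs all 26 doses and uniform scatter on a fixed grid.
- A reader might infer that scatter will be reported as treatment interruption. SAP 4.5.5 bases interruptions on investigator decisions and does not list total delay duration as an output.
- A reader might infer that the main safety result is biased. The primary endpoint is a proportion of patients and does not use exposure; RDI and PID are built from doses, not from this formula.

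Total exposure is also summarised beside actual exposure, so the gap between them will be visible.

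**Conclusion.** The point holds as a minor defect of definition. SAP 3.2.8 has no tolerance for the window and no allowance for a preceding early dose, so delay can be positive when no dose is late, and the zero-delay sentence fails for such a patient. The mechanism and direction need no assumption.

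The size does. Under the base case it is about 1.1 days per interval, reaching 3.9% of exposure at 26 doses and raising the AE rate by about 4.0%. On the same fixed grid with 72% of doses on the day, the rate rises by about 1.3%. The effect is confined to actual exposure and one descriptive rate, in a study that tests no hypothesis.

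**What to change.** In SAP 3.2.8, count as delay only the days beyond the permitted window: lateness past the scheduled day + 3 days. Restart the 28-day schedule from the first dose after a recorded hold, so that one hold is not counted again at each later dose. Also restart it after a realignment by shortened intervals, so that a later hold is not masked. State whether the analysis counts the window from the first or the previous dose. On a fixed grid this gives 0 for every patient within the window.

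At minimum, count only the part of an interval beyond 31 days. This is simpler but not complete, because a move from −3 to +3 makes a 34-day interval: the excess averages 10/49 = 0.204 days, and 24 × 0.204 = 4.9 days remain in the 26-dose base case, against 28.3 now.

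Do not apply a single maximum to the net sum over the course. It would cut the base case to 0.86 days but erase real holds that are later made up. Doses on Days 1, 43, 65, 87 and 113 (intervals 42, 22, 22, 26) contain a 14-day hold yet net to 112 − 4 × 28 = 0. Either tolerance rule records 11 days.

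The cost is one line of SAP text, with no new data. The downside is the one in that example: each true delay is counted up to 3 days shorter.

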**Table 5 Example dose intensity scenarios**

RDI	Patient	Study Day										
		1	29	57	85	113	141	169	197	225	230	
100%	1	X	X	X	X	X	X	X	X	X	X	PD
100%	2	X	X	X	X	X	X	X	X[D]			PD
56%	3	X		X		X	O	X	X			PD
67%	4	X	X	O	X	X	X	O	X	O		PD

X: Dose of 1500mg taken; O: Dose missed; [D]: Dose discontinued; PD: Progressive Disease

In this example, all 4 Patients progressed on Day 230, and so the intended dose through to progression was  $9 * 1500\text{mg}$  of durvalumab = 13500mg (13.5g).

Patient 1 received a total of 13.5g of durvalumab, whereas other patients received less durvalumab due to:

- Early stopping prior to PD (Patient 2)
- Dosing delays (Patient 3)
- Missed doses (Patient 4)

For RDI the examples of Patients 2 and 4 illustrate that the end of actual dosing period is calculated based on the smallest recovery period after the last non-zero dose.

Patient 1:  $\text{RDI} = (9 * 1.5\text{g}) / 13.5\text{g} = 100\%$

Patient 2:  $\text{RDI} = (8 * 1.5\text{g}) / 12\text{g} = 100\%$

Patient 3:  $\text{RDI} = (5 * 1.5\text{g}) / 13.5\text{g} = 56\%$

Patient 4:  $\text{RDI} = (6 * 1.5\text{g}) / 13.5\text{g} = 67\%$

For the examples the PID differs from RDI for Patient 2 where the calculation is based on the intended cumulative dose up to disease progression regardless treatment discontinuation.

Patient 1:  $\text{PID} = (9 * 1.5\text{g}) / 13.5\text{g} = 100\%$

Patient 2:  $\text{PID} = (8 * 1.5\text{g}) / 13.5\text{g} = 89\%$

Patient 3:  $\text{PID} = (5 * 1.5\text{g}) / 13.5\text{g} = 56\%$

Patient 4:  $\text{PID} = (6 * 1.5\text{g}) / 13.5\text{g} = 67\%$

Exposure will also be measured by the number of cycles (doses) of durvalumab received. If a

cycle is prolonged due to toxicity this will still be counted as one cycle. A cycle will be counted if treatment is started, even if the full dose is not delivered.

### 3.3 Efficacy Variables

All RECIST assessments, whether scheduled or unscheduled, and regardless of whether a patient discontinues durvalumab treatment or receives another anti-cancer therapy will be included in the calculation of efficacy variables.

#### 3.3.1 Progression-Free Survival

Progression-free survival is defined as the time from the date of first dose of durvalumab until the date of objective disease progression or death (by any cause in the absence of progression) regardless of whether the patient discontinues durvalumab or receives another anticancer therapy prior to progression.

- $PFS \text{ (days)} = (\text{date of PFS event or censoring}) - (\text{date of first dose of durvalumab}) + 1.$

Patients who have not progressed or died at the time of analysis will be censored at the date of their last evaluable tumour assessment (ie, this doesn't include NE or missing value).

If the patient progresses or dies after 2 or more missed visits, the patient will be censored at the date of the latest evaluable RECIST 1.1 assessment prior to the two missed visits.

Given the scheduled visit assessment scheme (i.e. eight-weekly for the first 48 weeks then twelve-weekly thereafter) the definition of 2 missed visits will change.

1. If the previous RECIST assessment is baseline then two missing visits will equate to 17 weeks since the previous RECIST assessment, allowing for a late visit (i.e.  $2 \times 8 \text{ weeks} + 1 \text{ week for a late assessment} = 17 \text{ weeks}$ ).
2. If the previous RECIST assessment is post baseline and less than study day 274 (i.e. week 39) then two missing visits will equate to 18 weeks since the previous RECIST assessment, allowing for early and late visits (i.e.  $2 \times 8 \text{ weeks} + 1 \text{ week for an early assessment} + 1 \text{ week for a late assessment} = 18 \text{ weeks}$ ).
3. If the two missed visits occur over the period when the scheduled frequency of RECIST assessments changes from eight-weekly to twelve-weekly this will equate to 22 weeks (i.e. take the average of 8 and 12 weeks which gives 10 weeks and then apply same rationale, hence  $2 \times 10 \text{ weeks} + 1 \text{ week for an early assessment} + 1 \text{ week for a late assessment} = 22 \text{ weeks}$ ). The time period for the previous RECIST assessment will be from study days 274 to 344 (i.e. week 39 to week 49).
4. From week 49 onwards (when the scheduling changes to twelve-weekly assessments), two missing visits will equate to 26 weeks (i.e.  $2 \times 12 \text{ weeks} + 1 \text{ week for an early assessment} + 1 \text{ week for a late assessment} = 26 \text{ weeks}$ ).

If the patient has no evaluable visits or does not have baseline data, he/she will be censored at Day 1 unless he/she dies within 2 visits of baseline, in which case the date of death is the event date.

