- $PFS \text{ (days)} = \text{Date of event or Censor date} - \text{treatment start date} + 1$
- Patients who have not progressed or died at the time of analysis will be censored at the time of the latest date of assessment from their last evaluable assessment. However, if the patient progresses or dies after 2 or more missed visits, the patient will be censored at the time of the latest evaluable assessment prior to the 2 missed visits. If the patient has no evaluable visits or does not have baseline data, he/she will be censored at Day 1 unless he/she dies within 2 visits of baseline, in which case the date of death is the event date.
- 8 **OS:** Defined as the time from the first date of treatment until death due to any cause.
- $OS \text{ (days)} = \text{Death date or Censor date} - \text{treatment start date} + 1$
- Any patient not known to have died at the time of analysis will be censored based on the last recorded date on which the patient was known to be alive.
- 9 **Lung cancer mortality (NSCLC-related death):** Defined as the time from the date of treatment start until death due to lung cancer.
- $\text{Time to NSCLC-related deaths (days)} = \text{NSCLC-related death date or Censor date} - \text{treatment start date} + 1$
- Any patient not known to have died due to lung cancer will be censored based on the last recorded date on which the patient was known to be alive or died due to reason other than lung cancer.
- 10 **ORR:** Based on Investigator-assessed response to treatment of CR and PR, per RECIST1.1.
- 11 **DoR:** Defined as the time from the date of first documented response per RECIST1.1 until the first date of documented progression per RECIST1.1 or death in the absence of disease progression

DoR (days) = Date of PFS event or censoring – Date of first response +1

The end of response should coincide with the date of progression or death from any cause used for the PFS endpoint. If a patient does not progress following a response, then the patients' DoR will be censored at the PFS censoring time. DoR will not be defined for those patients who do not have a documented response.

12

CCI [REDACTED]

13 **Treatment duration:** Defined as Treatment end date – Treatment start date +1; will be summarized.

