## **3. ANALYSIS VARIABLES**

### **3.1 Derivation of RECIST Visit Responses**

For all patients, the RECIST tumour response data will be used to determine each patient's visit response according to RECIST version 1.1. It will also be used to determine, if and when a patient's disease has progressed in accordance with RECIST and their best objective response to study treatment.

The baseline radiological tumour assessment is part of the screening procedure and should be performed within 42 days after the end of sCRT, no more than 28 days before the start of durvalumab treatment, and ideally as close as possible to the start of study treatment. Tumour assessments will begin at 8 weeks  $\pm$  1 week after durvalumab initiation and continue every 8 weeks  $\pm$  1 week through 52 weeks (relative to the date of durvalumab initiation), and then every 12 weeks  $\pm$  1 week thereafter until disease progression. An additional follow-up scan will be performed if clinically feasible.

If an unscheduled assessment is performed, and the patient's disease has not progressed, every attempt should be made to perform the subsequent assessments at patients' scheduled visits. This schedule is to be followed to minimise any unintentional bias caused by some patients being assessed at a different frequency than other patients.

Additional scans can be completed per standard practice post-disease progression.

From the investigator's review of the imaging scans, the RECIST tumour response data will be used to determine each patient's visit response according to RECIST version 1.1. At each visit, patients will be programmatically assigned a RECIST 1.1 visit response of CR, PR, SD or PD, using the information from target lesions (TLs), non-target lesions (NTLs) and new lesions and depending on the status of their disease compared with baseline and previous assessments. If a patient has had a tumour assessment which cannot be evaluated, then the patient will be assigned a visit response of not evaluable (NE) (unless there is evidence of progression in which case the

response will be assigned as PD).

RECIST outcomes (ie, PFS and ORR etc.) will be calculated programmatically from site investigator data from overall visit responses.

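### SAP 3.3.1 gives week-48 scans a 22-week limit instead of 26, so progressions and deaths after only one missed scan can be censored

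*SAP*

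**What the plan says.** Protocol 9.4 sets the principle without week limits: "if the patient progresses or dies after 2 or more missed visits, the patient will be censored" at the last evaluable assessment before the gap. SAP 3.3.1 repeats it ("If the patient progresses or dies after 2 or more missed visits, the patient will be censored") and adds four numerical rules, each counted from the previous RECIST assessment:

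- Rule 1, previous scan is baseline: "If the previous RECIST assessment is baseline then two missing visits will equate to 17 weeks since the previous RECIST assessment".
- Rule 2, post-baseline scan before day 274: 18 weeks.
- Rule 3, missed scans spanning the change in frequency: 22 weeks, built on the average of 8 and 12. "The time period for the previous RECIST assessment will be from study days 274 to 344 (i.e. week 39 to week 49").
- Rule 4, from week 49: 26 weeks.

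The rules assume scans "eight-weekly for the first 48 weeks then twelve-weekly thereafter". Table 1 of the protocol gives the ±1 week window: "On-study tumour assessments begin 8 weeks ±1 week after IP treatment initiation and continue q8w ±1 week through 52 weeks". SAP 3.1 allows the baseline scan to be "no more than 28 days before the start of durvalumab treatment". The last sentence of SAP 3.3.1 censors patients with no evaluable visit at Day 1, except that a death within two visits of baseline is an event. SAP 4.4.1 reports median PFS, PFS12 (Day 365) and PFS24 (Day 730). SAP 3.3.5 takes the end of response, or its censoring date, from PFS.

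**The concern.** Each week limit should be the longest gap that can arise before two scans have been missed. If a limit is too short for some scan position, events after a single missed scan are treated as if they followed two, and the patient is censored at the earlier scan. Rule 3's averaging suits a gap made of one 8-week and one 12-week interval. Its day range also takes in the week-48 scan, from which both following intervals are 12 weeks. At stake are a small upward shift in the later part of the PFS curve, the same error in duration of response for affected responders, and a programmed rule that departs from the principle stated in both documents. Rule 1 raises a related question, because its starting point is a scan that may precede first dose by up to four weeks.

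**Working it through.** **Inputs.** From SAP 3.3.1, scans fall at weeks 8, 16, 24, 32, 40, 48, then 60, 72, 84 and so on, each ±1 week. Study day = 7 × week + 1. This reproduces the SAP's day 274 (week 39) and day 344 (week 49), and puts week 47 at day 330. The week-48 window is therefore days 330 to 344.

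**Formula.** Limit = (nominal week of the second missed scan + 1) − (nominal week of the previous scan − 1), with no early week for baseline.

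| Previous scan | Next two scans | Formula | SAP limit |
|---|---|---|---|
| Day 1 | 8, 16 | 17 − 0 = 17 | 17 |
| Week 8 | 16, 24 | 25 − 7 = 18 | 18 |
| Week 32 | 40, 48 | 49 − 31 = 18 | 18 |
| Week 40 | 48, 60 | 61 − 39 = 22 | 22 |
| **Week 48** | **60, 72** | **73 − 47 = 26** | **22** |
| Week 60 | 72, 84 | 85 − 59 = 26 | 26 |

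The formula reproduces every stated limit except the one applied at week 48. Day 344 also falls under both rule 3 and rule 4.

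**One missed scan after week 48.** I read a limit as breached when the gap is longer than it; 22 weeks is 154 days. A scan in days 330 to 344, week 60 missed and progression in the week-72 window (days 498 to 512) give a gap of 498 − 344 = 154 to 512 − 330 = 182 days. The nominal gap is 505 − 337 = 168 days, or 24 weeks. Of the 15 × 15 = 225 allowed day pairs, 224 exceed 154 days. As a control, a week-40 scan with week 48 missed and progression at week 60 gives 414 − 288 = 126 to 428 − 274 = 154 days, and none of 225 pairs exceeds the limit. For deaths, with a scan on day 337 any death after day 337 + 154 = 491 is censored, although the week-72 window stays open to day 512.

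**Rule 1.** If the baseline scan is k days before Day 1, the gap to a progression on the nominal week-16 date (day 113) is 112 + k days. This exceeds 17 × 7 = 119 once k is 8 or more. For the earliest in-window date (day 106) the gap is 105 + k, so from k = 15 every in-window week-16 progression is over the limit although only week 8 was missed. At k = 28 the limit is passed from day 93. Counted from Day 1, the limit falls on day 120, the close of the week-16 window, and there is no error.

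**Size (simulation, assumed inputs).** Each setting used 400 trials of 120 patients, exponential PFS with median 10 or 16.8 months, 20% of events being deaths, scans missed at random, and the baseline scan 7 to 28 days before dosing. The table shows the week-48 error alone against the corrected rules; changes are in percentage points.

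| Missed scans | Median (months) | PFS12 | PFS24 | Events lost per 120 |
|---|---|---|---|---|
| 3% | 10 / 16.8 | −0.02 / −0.01 | +0.15 / +0.18 | 0.4 / 0.4 |
| 5% | 10 / 16.8 | −0.03 / −0.01 | +0.23 / +0.30 | 0.6 / 0.6 |
| 10% | 10 / 16.8 | −0.06 / −0.03 | +0.41 / +0.57 | 1.1 / 1.1 |
| 20% | 10 / 16.8 | −0.10 / −0.05 | +0.79 / +0.92 | 1.8 / 1.6 |

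If rule 1 is also counted from the scan date, the combined changes at 3% to 10% missed are about +0.2 to +0.7 for PFS12 and +0.3 to +0.9 for PFS24.

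**The case against.** The best defence concerns rule 1. It adds a late week but no early week, unlike rules 2 to 4, and 17 weeks is exactly right from Day 1. Censoring at a scan k days before dosing would also give a PFS of 1 − k days, zero or negative, so baseline was probably meant as Day 1. A reader might infer that rule 1 is simply wrong. The documents do not support that: the literal wording starts the count at the scan, but the intended anchor is unstated. What stands is the need to state it. The exception for deaths within two visits of baseline may already keep early deaths as events, though those two visits are not defined. It does nothing for a progression seen at an evaluable week-16 scan.

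A second defence is that the protocol's 8-weekly schedule runs through week 52, so the change of frequency may come later than week 48. This does not rescue rule 3. If the first 12-weekly scan were at week 64 and the next at week 76, the week-48 limit would have to be 77 − 47 = 30 weeks.

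A third defence is size, and it stands. No hypothesis is tested (Protocol 9.1), the primary endpoint is Grade 3 or 4 treatment-related events, and with 120 patients a proportion near 50% has a 95% half-width of about 1.96 × √(0.25/120) = 9 points, ignoring censoring.

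**Conclusion.** The week-48 limit is wrong on the SAP's own schedule, windows and formula: 22 weeks is applied where 26 is needed. The effect is modest, about 0.2 to 0.6 points on PFS24 at assumed missed-scan rates of 3% to 10%. The documents give no missed-scan rate, so the size is illustrative. Duration of response can inherit the error.

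Two stronger readings are tempting. One is that every PFS summary is pushed upwards. The week-48 error acts on events more than 22 weeks after that scan, well past Day 365. Censoring those patients at week 48 leaves PFS12 unchanged or at most 0.1 point lower. Any rise in PFS12 would come only from the literal reading of rule 1. The other is that several events per trial and about 1.5 points of PFS24 are at risk. That needs 20% of scans missed together with the literal reading of rule 1, and it pools a certain error with a disputed one.

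This should be fixed because a stated rule contradicts its own principle. It does not threaten the trial's main conclusions.

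**What to change.** In SAP 3.3.1:

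- Rule 3: limit it to a previous assessment on days 274 to 329 (22 weeks).
- Rule 4: apply 26 weeks to a previous assessment from day 330 (week 47) onwards. This also removes the overlap at day 344.
- Rule 1: state that the 17 weeks run from first dose, so that it applies when there is no post-baseline assessment and the event is after Day 120, and name Day 1 as the censoring date.
- No-evaluable-visits sentence: define the two-visit period for deaths so that it agrees with rule 1.

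Confirm at the same time that the first 12-weekly scan is at week 60, since the limits depend on it.

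The cost is a few lines of SAP text and the matching programming constants. Protocol 9.4 has no week limits, so this needs no protocol amendment. Any PFS or duration-of-response output already produced under these rules would need rerunning, and PFS24 may come out very slightly lower.
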